## 8.2. Dose Modification and Study Treatment Discontinuation Rules

### 8.2.1. Dose Modification

This is a single dose study; dose modification is not allowed.

### 8.2.2. Study Drug Discontinuation

This is a single dose study; study drug discontinuation is not applicable.

### **8.3. Management of Acute Reactions**

#### **8.3.1. Acute Injection Reactions**

##### **8.3.1.1. Systemic Injection Reactions**

Emergency equipment and medication for the treatment of systemic reactions must be available for immediate use. All injection reactions must be reported as AEs (as defined in Section 10.2.1) and graded using the grading scales as instructed in Section 10.2.4.

Acute systemic reactions following injection of study drug (subcutaneous [SC]) should be treated using clinical judgment to determine the appropriate response according to typical clinical practice.

##### **8.3.1.2. Local Injection Site Reactions**

Local injection site reactions must be reported as AEs and graded according to Section 10.2.4.

### **8.4. Method of Treatment Assignment**

Subjects will be randomized in a 1:1 ratio to receive REGN10987+REGN10933 or placebo according to a central randomization scheme provided by an interactive web response system (IWRS) to the designated study pharmacist (or qualified designee). Randomization will be performed by individual study subjects, not by households. In addition to a randomization number, all subjects randomized will be given a household identification number in the case that multiple members of the same household are enrolled and receive study drug. This ensures that any correlation among subjects within the same household may be considered in the statistical analysis. The REGN10987 and REGN10933 dose for adult, adolescent, and pediatric subjects is described in Section 8.1.

Randomization will be performed by site and stratified as follows:

- Local diagnostic assay for SARS-CoV-2 from appropriate samples (positive, negative, or undetermined)
- Age and/or weight:
  - <12 years and <10 kg,
  - <12 years and  $\geq$ 10 kg to <20 kg,
  - <12 years and  $\geq$ 20 kg
  - $\geq$ 12 years and <18 years
  - $\geq$ 18 years and <50 years
  - $\geq$ 50 years

Note that the cohorts used in the analysis are defined by the baseline central lab SARS-CoV-2 RT-qPCR results, not by the local diagnostic assay.

## 8.5. Blinding

Study subjects, the principal investigators, and study site personnel will remain blinded to all randomization assignments throughout the study. The Regeneron Medical/Study Director, Study Monitor, and any other Regeneron and contract research organization (CRO) personnel who are in regular contact with the study sites will remain blinded to all subject randomization assignments.

No interim analyses were conducted (Section 11.5) and an unblinded administrative assessment of study assumptions (Section 11.2) was conducted. No study personnel involved in the day-to-day conduct of the study will have access to any subject-level unblinded data before the final database is locked for this study.

Anti-drug antibody, drug concentration results, and central lab serology results will not be communicated to the sites. The Sponsor's blinded study team will not have access to post-baseline results associated with subject identification until after the database is locked for the respective study part.

## 8.6. Emergency Unblinding

Unblinding of treatment assignment for a subject may be necessary due to a medical emergency or any other significant medical event and when a treatment decision is contingent on knowing the subject's treatment assignment.

- If unblinding is required:
  - Only the investigator will make the decision to unblind the treatment assignment.
  - Only the affected subjects will be unblinded.
  - The designated study pharmacist(s)/designee at the study site will provide the treatment assignment to the investigator. If there is no study pharmacist, the investigator for the site will unblind the subject. Unblinding is performed using the IVRS/IWRS which will notify Regeneron.
- The investigator will notify Regeneron and/or designee as soon as possible after unblinding the subject for safety or other important medical decisions, however, unblinding performed for the purpose of COVID-19 vaccine decision making does not need to be discussed with the medical director.

Treatment assignment is not to be provided to site personnel, other than the unblinded study pharmacist (when applicable), at any time during the conduct of the study, except in the case of a true emergency and when a treatment decision is contingent on knowing the subject's treatment assignment. In the event that there is no study pharmacist, the individual at the site fulfilling that role will be the only unblinded member of the site personnel.

## 8.7. Treatment Logistics and Accountability

### 8.7.1. Packaging, Labeling, and Storage

A medication numbering system will be used to label blinded investigational study drug. Lists linking medication numbers with product lot numbers will be maintained by the groups (or companies) responsible for study drug packaging. In order to maintain the blind, these lists will not be accessible to individuals involved in study conduct.

Study drug will be stored at the site at a temperature of 2°C to 8°C; storage instructions will be provided in the pharmacy manual.

### 8.7.2. Supply and Disposition of Treatments

Study drug will be shipped at a temperature of 2°C to 8°C to the investigator or designee at regular intervals or as needed during the study. At specified time points during the study (eg, interim site monitoring visits), at the site close-out visit, and following drug reconciliation and documentation by the site monitor, all opened and unopened study drug will be destroyed at the site with approval by the Sponsor or returned to the Sponsor or designee.

### 8.7.3. Treatment Accountability

All drug accountability records must be kept current.

The investigator must be able to account for all opened and unopened study drug. These records should contain the dates, quantity, and study medication

- dispensed to each subject
- disposed of at the site or returned to the sponsor or designee.

All accountability records must be made available for inspection by the sponsor and regulatory agency inspectors; photocopies must be provided to the sponsor at the conclusion of the study.

### 8.7.4. Treatment Compliance

All drug compliance records must be kept current and made available for inspection by the Sponsor and regulatory agency inspectors.

## 8.8. Concomitant Medications and Procedures

Any treatment administered from the single dose of study drug to final study visit will be considered concomitant medication. This includes medications that were started before the study and are ongoing during the study.

As per Section 6.1.4 and Section 6.1.5, a positive SARS-CoV-2 test which is associated with a symptomatic SARS-CoV-2 infection and is conducted in a local laboratory associated with a medical facility, should be recorded as a concomitant procedure and associated with the COVID-19 AE.

## 8.9. Prohibited Medications

Treatment with the following concomitant medications as prophylaxis is prohibited in uninfected subjects or for treatment of asymptomatic infection during the EAP and Follow-Up Period and may result in permanent discontinuation from the study.

1. Other investigational drugs
2. Investigational SARS-CoV-2 vaccine
3. Approved or EUA approved SARS-CoV-2 vaccine (prohibited only during the EAP)
4. Investigational or approved passive antibodies for SARS-CoV-2 infection prophylaxis (eg, convalescent plasma or sera, monoclonal antibodies, hyperimmune globulin)
5. Hydroxychloroquine/chloroquine prescribed for the prophylaxis or treatment of COVID19 (*Note Hydroxychloroquine/chloroquine used for other indications eg, autoimmune therapies are permitted.*)
6. Remdesivir or anti-SARS-viral agents

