Adult and adolescent subjects in cohort B (ie, asymptomatic subjects who are SARS-CoV-2 RT-qPCR positive at baseline, irrespective of the serology status being positive or negative) will be analyzed separately from cohort A with a primary study objective and endpoint, secondary and exploratory objectives and endpoints. The primary efficacy objective in cohort B is focused on the prevention of COVID-19 symptoms (broad-term) in the subjects who are seronegative but

SARS-CoV-2 RT-qPCR positive at baseline. The analysis of the adult and adolescent subject populations that are not part of the primary study population of interest (ie, those subjects in cohort B who are seropositive at baseline) will not contribute to a primary study objective or endpoint. These individuals will be analyzed separately either through secondary or exploratory objectives and endpoints.

Pediatric subjects (<12 years) will be divided into 2 independent study cohorts, cohort A1 or cohort B1. This allocation will be based on a central lab SARS-CoV-2 RT-qPCR test result performed during the screening/baseline visit.

To mitigate enrollment of a high percentage of subjects that are either seropositive or SARS-CoV-2 RT-qPCR positive at baseline, those with a known prior history of a positive SARS-CoV-2 RT PCR test, a positive serology test, or COVID-19 will be excluded.

All subjects' SARS-CoV-2 qualitative diagnostic and RT-qPCR test results will be unblinded during the study. This will ensure SARS-CoV-2 infected individuals take the appropriate precautions necessary to prevent spread of disease. However, all subjects' SARS-CoV-2 serology results will remain blinded to study site personnel during the study to avoid potential bias introduced when evaluating and assessing subjects who are seropositive and to avoid encouraging higher risk behaviors through disclosure of seropositivity.

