### 7.3. Premature Withdrawal from the Study

A subject or pediatric subject's parent/guardian has the right to withdraw from the study at any time, for any reason, and without repercussion.

The investigator and/or Sponsor have the right to withdraw a subject from the study if it is no longer in the interest of the subject to continue in the study, or if the subject's continuation in the study places the scientific outcome of the study at risk (eg, if a subject does not or cannot follow study procedures). An excessive rate of withdrawals would render the study uninterpretable; therefore, unnecessary withdrawal of subjects should be avoided.

Subjects who are withdrawn prematurely from the study will be asked to complete the ET visit, as described in Section 9.1.5.

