### 7.4. Replacement of Subjects

Subjects prematurely discontinued from study will not be replaced.

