## 8.10. Permitted Medications

Other than the prohibited medications listed in Section 8.9, treatment with concomitant medications is permitted during the study. If there is any question regarding whether a concomitant medication may be used during the study, the study site should contact the medical monitor.

Subjects with symptomatic RT-qPCR confirmed SARS-CoV-2 infection during the study will be treated according to local standard of care as per the discretion of the investigator or treating physician. Any medication used by the study subject should be captured in the concomitant medication eCRF.

Subjects are permitted to receive an approved or EUA approved COVID-19 vaccine after they complete the EAP.

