**9.1.5. Early Termination Visit**

Subjects who are withdrawn from the study will be asked to provide final blood samples for drug concentration and immunogenicity analysis.

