10. APPENDIX

10.1. Summary of Statistical Analyses

Primary Efficacy Analysis:

Endpoint	Analysis Population	Estimand	Statistical Method	Supportive Analysis	Subgroup Analysis	Other Analyses
Proportion of subjects who have a symptomatic RT-qPCR confirmed SARS-CoV-2 infection (broad-term) during the EAP	Seronegative mFAS-A	A broad-term symptom occurring within a 14-days window of any positive RT-qPCR during the EAP regardless of adherence to study treatment will be included for the primary analysis.	A generalized linear model with the generalized estimation equation (GEE) approach or logistic regression. If percent of households with single study subject greater than or equal to 70%. Missing RT-qPCR will be imputed as positive RT-qPCR if a subject with COVID-19 signs and symptoms (broad-term) occurring within a 14-day window of a visit with missing RT-qPCR data.	Yes	Yes	
 1. Excluding those subjects who develop asymptomatic or symptomatic SARS-CoV-2 infection within 72 hours of the study drug administration 2. Exclude subjects from non-GCP compliance sites
Proportion of subjects who have a symptomatic RT-qPCR confirmed SARS-CoV-2 infection (broad-term) at baseline or during the EAP	Seronegative mFAS-B	Same as above including a positive RT-qPCR at baseline	Same as above including a positive RT-qPCR at baseline	Yes	No	
 1. Exclude subjects from non-GCP compliance sites

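### Section 8.9 allows removal from the study for taking a prohibited agent, which in a one-dose trial ends only data collection and leaves the subject a default non-event in the primary analysis

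*Protocol*

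**What the plan says.** Protocol 8.9 lists other investigational drugs, SARS-CoV-2 vaccines (an approved or EUA vaccine only during the EAP), passive antibodies, hydroxychloroquine or chloroquine for COVID-19, and antivirals. It bars them as prophylaxis in uninfected subjects or "for treatment of asymptomatic infection during the EAP and Follow-Up Period and may result in permanent discontinuation from the study". Section 8.10 takes subjects who are already symptomatic out of the rule: "Subjects with symptomatic RT-qPCR confirmed SARS-CoV-2 infection during the study will be treated according to local standard of care".

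The surrounding provisions are these:

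- Protocol 8.2.2: "This is a single dose study; study drug discontinuation is not applicable".
- Protocol 7.3, on withdrawal: "unnecessary withdrawal of subjects should be avoided". Protocol 7.4: "Subjects prematurely discontinued from study will not be replaced".
- Protocol 9.1.5: withdrawn subjects "will be asked to provide final blood samples for drug concentration and immunogenicity analysis". No later swab or symptom follow-up is described.
- Protocol 3.2.3: "All subjects' SARS-CoV-2 qualitative diagnostic and RT-qPCR test results will be unblinded during the study".
- SAP 4.4 and 5.4: prohibited medication is reported among the protocol deviations and listed. No exclusion or censoring is attached to it.
- SAP 10.1, estimand for the cohort A primary endpoint: a broad-term symptom within 14 days of a positive PCR "regardless of adherence to study treatment will be included for the primary analysis". Cohort B follows the same line, with the baseline PCR added.

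**The concern.** In a multi-dose trial, discontinuing someone for a prohibited drug can at least mean stopping study drug. Here nothing is left to stop, so removal has one effect on the analysis: the remaining observations are not collected.

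The missing observations need not be missing at random. PCR results are disclosed, so a subject can learn of a positive test while still symptom-free, obtain one of the listed agents and be withdrawn before any symptom is recorded. Some of those subjects would have become primary events. Every subject in the cohort B analysis set is in that position at baseline; in cohort A only those who turn positive without symptoms are.

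At stake are some lost events, a smaller risk difference, some loss of power, and a primary result that depends partly on a discretionary withdrawal decision.

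**Working it through.** **Step 1. How a removed subject is scored.**

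- Protocol 11.3.1 and SAP 3.1 keep all randomized subjects who meet the baseline PCR and serology criteria (outside the administrative assessment for cohort A), so withdrawal does not take a subject out of the analysis.
- Protocol 11.4.3.1 and SAP 5.7.1 require a symptom within 14 days of a positive PCR.
- The missing-PCR rule in those sections needs symptoms plus a positive local test. SAP 10.1 words it differently and imputes a positive for symptoms near a missing PCR. Both versions need symptoms.
- Multiple imputation (Protocol 11.4.3.2, SAP 5.7.3) applies to the key secondary infection endpoint only.
- The synopsis says that missing-data sensitivity analyses are in the protocol. Section 11.4.3.1.1 and SAP 5.7.1.1 contain only the 72-hour and non-GCP-site exclusions.

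A subject who leaves before symptoms are recorded therefore meets no event criterion and no imputation rule. Scoring as no event is an inference; no section says it in words.

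**Step 2. Reproduce the plan's power.** Inputs from Protocol 11.2.1 and 11.2.2: cohort A 10% v 5%, 1248 subjects at 1:1 (624 per arm); cohort B 50% v 25%, 200 subjects (100 per arm); two-sided 0.05.

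For cohort A, treating subjects as independent, power = Φ[(d − 1.96·SE0)/SE1], where SE0 uses the pooled rate and SE1 the separate rates:

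- d = 0.05; SE0 = √(2 × 0.075 × 0.925/624) = 0.01491; SE1 = √((0.0900 + 0.0475)/624) = 0.01484.
- (0.05 − 0.02923)/0.01484 = 1.40, giving power 0.919. Table 9 states 0.914 at correlation 0.1.

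Cohort B, exact two-sided Fisher test: 0.945, against a stated >90%. Enrolment: 1980 × 0.9 × 0.7 = 1247, against 1248. The plan's figures reproduce.

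**Step 3. Lose an equal share of events.** Let q be the share of would-be events lost in each arm. The documents give no q; 5% to 20% is an assumption. Both rates are multiplied by (1 − q), so the relative risk stays 0.50 and the risk difference shrinks by q. For cohort A at q = 10% (9% v 4.5%): SE0 = 0.01420, SE1 = 0.01415, (0.045 − 0.02784)/0.01415 = 1.21, power 0.89.

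| q | Cohort A, 624 per arm | Cohort A, 693 per arm | Cohort B, 100 per arm |
|---|---|---|---|
| 0 | 0.919 | 0.943 | 0.945 |
| 5% | 0.904 | 0.931 | 0.925 |
| 10% | 0.887 | 0.917 | 0.902 |
| 20% | 0.846 | 0.881 | 0.844 |

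The 693 column matters because 1248 is already net of 10% dropout, while withdrawn subjects stay in the analysis set. Before that deduction there are 1980 × 0.7 = 1386 seronegative subjects, or 693 per arm. Applying q to 624 counts the loss twice. A GEE simulation with household correlation 0.1 agrees with the 624 column: 0.892 at q = 10% and 0.848 at 20%.

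**Step 4. How many removed positives would have been events.** In the administrative assessment 8 placebo subjects had symptomatic infection (Protocol 3.2.5) and 21 were infected (3.2.6): 8/21 = 38%. Cohort B assumes 50% on placebo.

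**The case against.** The other side has real force on size. Section 8.9 is permissive and 7.3 leans against withdrawal. The SAP neither excludes nor censors users of prohibited medication. Protocol 1.5 says that nothing is approved for infected but asymptomatic people and describes the antibody authorizations as being for outpatients at high risk, so few asymptomatic subjects may obtain such an agent. In cohort A, symptoms may precede the first positive PCR by up to 14 days (9.2.2.2) and central results wait on shipping (3.2.1), so many cases are never known to be positive while symptom-free. Use in the follow-up period can hardly touch the primary endpoint. All of this stands, and it argues for a small q. It gives no reason to end data collection when no treatment is being stopped.

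Three stronger readings are tempting, and the documents do not support them:

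- **That 8.9 contradicts the stated estimand.** SAP 10.1 speaks of adherence to study treatment, which is one dose given on site. It does not address prohibited medication or study withdrawal. The rule sits poorly with a treatment-policy reading, but the estimand is silent rather than contradicted.
- **That removal would be heavier on placebo and bias the relative risk.** More placebo subjects were PCR-positive at day 8 (10.3% v 5.4%), so more would be exposed to the rule, but that does not raise the share removed. Sites and subjects are blinded (8.5), and in cohort B both arms are entirely positive at baseline. Section 8.6 does foresee unblinding for vaccine decisions, which is a reason to report withdrawals by arm, not evidence of a difference.
- **That power above 90% is lost in both cohorts.** At q = 10%, cohort B keeps 0.90 and cohort A about 0.92 once dropout is not counted twice.

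**Conclusion.** The point holds as an avoidable, possibly outcome-related loss of primary data, with cohort B most exposed. It sits poorly with 7.3, with SAP 4.4 and with a treatment-policy reading of SAP 10.1. Its size cannot be established, because removal is discretionary and no rate of use or withdrawal is given. A removed asymptomatic positive on placebo would have become an event in roughly 38% to 50% of cases, not in every case.

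Under equal loss the relative risk is unchanged, the risk difference shrinks by q, and the cost in power is modest: about 3 to 4 points at q = 10% and 6 to 10 points at q = 20%. Equal loss does not manufacture efficacy. These figures rest on the plan's own rates, on independent subjects for the cohort A formula, and on an assumed q. It is worth correcting because the remedy is cheap, not because the loss is shown to be large.

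**What to change.** **Protocol.** In 8.9, replace the closing clause on permanent discontinuation with: use will be recorded as a protocol deviation, and the subject remains in the study for all remaining swabs, symptom queries and safety visits. In 7.3, add that use of a prohibited medication is not by itself a reason for withdrawal. The list of prohibited agents stays as it is.

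**SAP.** Name prohibited-medication use in the 10.1 estimand as an intercurrent event handled by treatment policy. Report withdrawals under 8.9 by arm and cohort. Add a primary-endpoint sensitivity analysis for early withdrawal, and align the missing-PCR wording in 5.7.1 and 10.1. Protocol 11.4.9 describes EAP data as already collected for subjects randomized by 28 Jan 2021; for subjects whose EAP is complete, the SAP changes are the useful ones.

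**Cost.** One sentence in each of two protocol sections, a few lines and one added analysis in the SAP, and no visits beyond those scheduled. The downside is that some retained subjects will have taken other agents, which a treatment-policy approach accepts.

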## 8.10. Permitted Medications

Other than the prohibited medications listed in Section 8.9, treatment with concomitant medications is permitted during the study. If there is any question regarding whether a concomitant medication may be used during the study, the study site should contact the medical monitor.

Subjects with symptomatic RT-qPCR confirmed SARS-CoV-2 infection during the study will be treated according to local standard of care as per the discretion of the investigator or treating physician. Any medication used by the study subject should be captured in the concomitant medication eCRF.

Subjects are permitted to receive an approved or EUA approved COVID-19 vaccine after they complete the EAP.

## 9. STUDY SCHEDULE OF EVENTS AND PROCEDURES

### 9.1. Schedule of Events

Study assessments and procedures for adult and adolescent subjects and pediatric subjects <12 years old are presented by study period and visit in [Table 3](#) and [Table 5](#) for the period from screening/baseline to end of the EAP and the Follow-up Period, and in [Table 4](#) and [Table 6](#) for sample collection for assay of drug concentration and ADA, as well as for safety clinical labs during the entire study.

Refer to Section [6.1.4](#) for conducting study assessments and sample collection when a subject is positive for SARS-CoV-2 infection based on rapid RT-PCR or RT-qPCR and when a subject is hospitalized.

